11.3 Analysis of Laboratory and Vital Signs Data

Data collected from the central and local laboratories, including additional laboratory testing due to an SAE, will be used in all analyses.

The value for baseline used in laboratory and vital sign analyses is defined in Section 6.0. Post baseline visits windows are specified in Table 3.

Hematology variables include: hematocrit, hemoglobin, red blood cell (RBC) count, white blood cell (WBC) count, neutrophils, lymphocytes, platelet count, and reticulocyte count.

Chemistry variables include: blood urea nitrogen (BUN), creatinine, total bilirubin, alanine aminotransferase (ALT), aspartate aminotransferase (AST), alkaline phosphatase, sodium, potassium, calcium, inorganic phosphorus, uric acid, glucose, albumin, Lactate dehydrogenase (LDH).

Mean changes from baseline at each scheduled post-baseline visit will be summarized with the baseline mean, visit mean, change from baseline mean, standard deviation, and median.

11.3.1 Analyses of Shift from Baseline in Clinical Laboratory Data

For shifts relative to National Cancer Institute Common Toxicity Criteria for Adverse Events (NCI CTCAE version 4.0), baseline and post-baseline laboratory observations (maximum and final) will be categorized as grade 0, grade 1, grade 2, grade 3, or grade 4 according to NCI CTCAE grade version 4.0.

The baseline and final grades will be defined respectively as the grade of the last measurement collected prior to the first dose of venetoclax unless specified differently in Section 6.0, and as the last post-baseline measurement collected no more than 30 days after the last dose of venetoclax.

The maximum NCI toxicity grade value is the value with highest NCI toxicity grade collected after the first dose of venetoclax and within 30 days following the last dose of venetoclax. In cases where multiple values are collected on the same day, the maximum grade value will be selected as the value for that day.

For each variable, shift tables will be generated that cross tabulate the number of subjects with baseline values of grade 0, grade 1, grade 2, grade 3, or grade 4 versus maximum or final observations of grade 0, grade 1, grade 2, grade 3, grade 4 or grade 5.

Detailed listings of data for subjects experiencing NCI CTCAE grade 3 to 4 blood chemistry and hematology values will be provided. All measurements collected, regardless of the number of days after the last dose of venetoclax, will be included in these listings.

Potential Drug-Induced Liver Injury (DILI)

Potential DILI will be determined by searching post-dose laboratory ALT or AST $> 3 \times \text{ULN}$ in combination with total bilirubin $> 2 \times \text{ULN}$ that occur within 72 hours of each other.

11.3.2 Assessment of Potentially Clinically Significant Vital Signs Values

Vital sign variables are systolic blood pressure, diastolic blood pressure, heart rate, and body temperature.

Pre-defined criteria for potentially clinically significant vital signs values are given in [Table 4](#):

Table 4. Criteria for Potentially Clinically Significant Laboratory Values – Vital Signs Variables

Vital Signs Variables	Criterion	Definition of Potentially Clinically Significant
Systolic blood pressure	High	Value ≥ 160 mmHg
Diastolic blood pressure	High	Value ≥ 100 mmHg
Heart rate	Low	Value < 50 bpm
	High	Value ≥ 120 bpm
Temperature	Low	Value $< 36^\circ\text{C}$
	High	Value $\geq 38.5^\circ\text{C}$

The number and percentage of subjects who have at least one post-baseline observation meeting the pre-defined criteria for potentially clinically significant values will be provided for each vital sign. A listing of all observations collected will be generated for

subjects that had at least one post-baseline observation meeting pre-defined criteria for potentially clinically significant values.

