At each visit, including the Final Visit and the Post-Treatment Follow Up, the subject's medical history will be reviewed and any changes from baseline will be recorded on the adverse event eCRF.

If a subject reports taking any over-the-counter or prescription medications, vitamins and/or herbal supplements or if administration of any medication becomes necessary

beginning with Screening through the end of the study, the name of the medication, dosage information including dose, route and frequency, date(s) of administration including start and end dates, and reason for use must be recorded on the appropriate eCRF.

Vital Signs

Vital signs include body temperature (oral or tympanic), weight, blood pressure and pulse. On days when venetoclax is administered in the clinic, blood pressure and pulse rate will be measured after the subject has been sitting for at least 5 minutes.

NOTE: Starting with visit Week 8 Day 1, vital signs may be performed within 72 hours before or after the scheduled visit.

Physical Examination

At Screening, the subject should have a **complete physical examination**, including height and weight (height only performed during Screening). A complete physical examination should include the evaluation of head, eyes, ears, nose and throat (HEENT); cardiovascular, dermatological, musculoskeletal, respiratory, gastrointestinal and neurological systems.

A **symptom directed physical examination** may be performed at all other visits (other than screening) and should be limited to systems of primary relevance: cardiovascular, respiratory, and those associated with symptoms.

Physical Examination (Disease Assessment)

Physical examinations performed as a part of Disease Assessments (Screening, Weeks 24, 36, 48) are to include the evaluation of the presence and degree of enlarged lymph nodes in two dimension (cervical, supraclavicular, axillary, inguinal and femoral nodes), hepatomegaly, and splenomegaly. These lymph node evaluations should be noted on all physical examinations irrespective of being present or absent. Refer to Disease

Assessments (2008 Modified IWCLL NCI-WG Criteria) for additional information pertaining to methods of measurement.

Changes from baseline abnormalities should be recorded at each subsequent physical examination. New or worsened abnormalities should be recorded as AEs if appropriate.

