Computed tomography (CT) is the preferred method to measure lesions selected for response assessment. CT scans (with contrast) should include neck, chest, abdomen, and pelvis scans. CT scans for response assessment may be limited to areas of prior involvement only, if required by local regulatory authorities. A contrast-enhanced MRI of the neck, chest, abdomen and pelvis with a non-contrast CT scan of the chest may be used if CT with contrast is medically contraindicated (e.g., severe contrast allergy). If MRIs are used instead of CT scans, MRIs should be used consistently throughout the study. Conventional CT and MRI should be performed with cuts of 5 mm or less in slice thickness contiguously. Spiral CT should be performed by use of 5 mm contiguous reconstruction algorithm; this specification applies to the regions of the neck, chest, abdomen and pelvis at baseline and follow ups. The 12 largest bi-dimensional lesions should be recorded in the eCRF (6 nodal and 6 extra nodal).

For accurate overall response evaluation, ultrasound (US) should not be used to measure tumor lesions.

Details on bone marrow biopsy and aspirate are provided in Section 5.3.1.1. Study Procedures.

Tumor Response Criteria

Complete Remission (CR)

CR requires all of the following criteria:

- Peripheral blood lymphocytes (evaluated by blood and differential count) below $4 \times 10^9/L$ (4000/ μ L)
- Absence of lymphadenopathy (nodes > 15 mm in longest diameter or any extra nodal disease) by physical examination and CT scan

- No hepatomegaly or splenomegaly by physical examination (as determined by measurement below the relevant costal margin)
- Absence of disease or constitutional symptoms (B symptoms: unexplained fevers > 38°C or 100.4°F, drenching night sweats, > 10% body mass weight loss in the preceding 6 months)
- Blood counts above the following laboratory values:
 - Neutrophils > $1.5 \times 10^9/L$ [1500/ μ L] (without the need for exogenous growth factors)
 - Platelets > $100 \times 10^9/L$ [100,000/ μ L] (without the need for platelet transfusion or exogenous growth factors)
 - Hemoglobin > 110 g/L [11 g/dL] (without the need for blood transfusions or exogenous erythropoietin)

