6.1.1 Definitions

6.1.1.1 Adverse Event

An adverse event (AE) is defined as any untoward medical occurrence in a subject or clinical investigation subject administered a pharmaceutical product and which does not necessarily have a causal relationship with this treatment. An adverse event can therefore be any unfavorable and unintended sign (including an abnormal laboratory finding), symptom, or disease temporally associated with the use of a medicinal (investigational) product, whether or not the event is considered causally related to the use of the product.

Such an event can result from use of the drug as stipulated in the protocol or labeling, as well as from accidental or intentional overdose, drug abuse, or drug withdrawal. Any worsening of a pre-existing condition or illness is considered an adverse event.

Worsening in severity of a reported adverse event should be reported as a new adverse event. Laboratory abnormalities and changes in vital signs are considered to be adverse events only if they result in discontinuation from the study, necessitate therapeutic medical intervention, meets protocol specific criteria (see Section 6.1.9 Toxicity Management) or if the investigator considers them to be adverse events.

For this protocol, disease progression is an efficacy endpoint. These data will be captured as efficacy assessment data only. Thus, events that are clearly consistent with the expected pattern of progression of the underlying disease (such as transformation to more aggressive histology) will result in discontinuation from the study and should not be recorded as adverse events but reported on the Study Completion eCRF. However, if a subject experiences an adverse event (e.g., pneumonia, pyrexia, fatigue, etc.) and is also found to have disease progression, report the adverse event. If there is any uncertainty as to whether an event is due to disease progression, it should be reported as an adverse event.

An elective surgery/procedure scheduled to occur during a study will not be considered an adverse event if the surgery/procedure is being performed for a pre-existing condition and the surgery/procedure has been pre-planned prior to study entry. However, if the

pre-existing condition deteriorates unexpectedly during the study (e.g., surgery performed earlier than planned), then the deterioration of the condition for which the elective surgery/procedure is being done, will be considered an adverse event.

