Appendix F. Definitions of Laboratory and Clinical Tumor Lysis Syndrome

Metabolic Abnormality	Criteria for Classification of Laboratory Tumor Lysis Syndrome	Criteria for Classification of Clinical Tumor Lysis Syndrome
Hyperruricemia	Uric acid > 8.0 mg/dL (475.8 µmol/liter) in adults or above the upper limit of the normal range for age in children	
Hyperphosphatemia	Phosphorus > 4.5 mg/dL (1.5 mmol/liter) in adults or > 6.5 mg/dL (2.1 mmol/liter) in children	
Hyperkalemia	Potassium > 6.0 mmol/liter	Cardiac dysrhythmia or sudden death probably or definitely caused by hyperkalemia
Hypocalcemia	Corrected calcium < 7.0 mg/dL (1.75 mmol/liter) or ionized calcium < 1.12 (0.3 mmol/liter) [†]	Cardiac dysrhythmia, sudden death, seizure, neuromuscular irritability (tetany, paresthesias, muscle twitching, carpopedal spasm, Trousseau's sign, Chvostek's sign, laryngospasm, or bronchospasm), hypotension, or heart failure probably or definitely caused by hypocalcemia
Acute kidney injury [‡]	Not applicable	Increase in the serum creatinine level of 0.3 mg/dL (26.5 µmol/liter) (or a single value > 1.5 times the upper limit of the age-appropriate normal range if no baseline creatinine measurement is available) or the presence of oliguria, defined as an average urine output < 0.5 mL/kg/hr for 6 hrs

[†] The corrected calcium level in milligrams per deciliter = measured calcium level in milligrams per deciliter + 0.8 × (4-albumin in grams per deciliter).

[‡] Acute kidney injury is defined as an increase in the creatinine level of at least 0.3 mg per deciliter (26.5 µmol per liter) or a period of oliguria lasting 6 hours or more. By definition, if acute kidney injury is present, the subject has clinical tumor lysis syndrome. Data about acute kidney injury from Levin et al.

Note: In laboratory tumor lysis syndrome, two or more metabolic abnormalities must be present during the same 24-hour period within 3 days before the start of therapy or up to 7 afterward. Clinical tumor lysis syndrome requires the presence of laboratory tumor lysis syndrome plus an increased creatinine level, seizures, cardiac dysrhythmia, or death.

Appendix G. Recommendations for Initial Management of Electrolyte Abnormalities and Prevention of Tumor Lysis Syndrome (TLS)

Section 1: First Dose of Venetoclax or Dose Escalation

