- Within the first 24 hours after either the first dose or dose escalation, if any laboratory criteria below are met, the subject should be hospitalized for monitoring and the investigator notified. No additional venetoclax doses should be administered until resolution. Rapidly rising serum potassium is a medical emergency.
- Nephrology (or other acute dialysis service) should be contacted/consulted (per institutional standards to ensure emergency dialysis is available) on admission for any subject hospitalized prophylactically or in response to laboratory changes.
- IV fluids (e.g., D5 1/2 normal saline) should be initiated at a rate of at least 1 mL/kg/hr rounded to the nearest 10 mL (target 150 to 200 mL/hr; not < 50 mL/hr). Modification of fluid rate should also be considered for individuals with specific medical needs.
- Monitor for symptoms or signs of TLS (e.g., fever, chills, tachycardia, nausea, vomiting, diarrhea, diaphoresis, hypotension, muscle aches, weakness, paresthesias, mental status changes, confusion and seizures). If any clinical features are observed, recheck potassium, phosphorus, uric acid, calcium and creatinine within 1 hour STAT.
- Vital signs should be taken at time of all blood draws or any intervention.
- The management recommendations below focus on the minimum initial responses required. If a diagnosis of TLS is established, ongoing intensive monitoring and multi-disciplinary management will be per institutional protocols.

In addition to the recommendations in the table below, for subjects receiving the first dose of venetoclax.

- For potassium increase ≥ 0.5 mmol/L from baseline, or any value > 5.0 mmol/L, recheck potassium, phosphorus, uric acid, calcium and creatinine within 1 hour STAT and follow first guideline.
- For phosphorus increase of > 0.5 mg/dL AND > 4.5 mg/dL, administer phosphate binder and recheck potassium, phosphorus, uric acid, calcium and creatinine within 1 hour STAT.

Abnormality	Management Recommendations
Hyperkalemia (Including Rapidly Rising Potassium)	

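### SAP Table 4 flags blood pressure only when it is high, so the threshold count cannot show low readings, although the protocol names hypotension as a sign of tumor lysis syndrome

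*SAP*

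**What the plan says.** SAP 11.3.2 defines the vital-sign analysis set: "Vital sign variables are systolic blood pressure, diastolic blood pressure, heart rate, and body temperature". Table 4 sets the limits. For systolic pressure the only entry is in the high direction, "Value ≥ 160 mmHg". For diastolic pressure it is again high only, "Value ≥ 100 mmHg". Heart rate has a low limit (below 50 bpm) and a high limit (120 bpm or more). Temperature has a low limit (below 36 °C) and a high limit (38.5 °C or more).

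Two outputs follow from the table. One is the number and percentage of subjects with at least one post-baseline value meeting a limit. The other is a listing of all observations, restricted to subjects who met at least one limit.

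The protocol collects blood pressure as a routine vital sign (Section 5.3.1.1, Vital Signs). Appendix D schedules vital signs at every visit from Screening to the 30-day safety visit. Appendix G, Section 1 includes hypotension in its examples of TLS signs to monitor, and adds for that setting: "Vital signs should be taken at time of all blood draws or any intervention". Appendix F, in the clinical column of the hypocalcemia row, includes "hypotension, or heart failure probably or definitely caused by hypocalcemia". The hypocalcemia row of the Appendix G table gives hypotension as an example symptom too.

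**The concern.** A threshold table exists to show individual extreme values that averages hide and that do not depend on an investigator deciding to report them. For blood pressure, the plan applies this tool in one direction only. The direction left out is the one that the protocol links to TLS, which is an adverse event of special interest in Protocol 6.1.1.4 and in SAP Table 3.

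At stake is the usefulness of one safety display. The trial has a single arm, so readers of the report will look to displays of this kind for a plain account of what was measured. On low blood pressure this one will be silent, although the readings are in the database.

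**Working it through.** The plan states no figure to reproduce, and no sample-size or power calculation bears on the point. The check is a reading of the rule.

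**Step 1: limits in SAP Table 4.**

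| Variable | Low limit | High limit |
|---|---|---|
| Systolic pressure | none | ≥ 160 mmHg |
| Diastolic pressure | none | ≥ 100 mmHg |
| Heart rate | < 50 bpm | ≥ 120 bpm |
| Temperature | < 36 °C | ≥ 38.5 °C |

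Four variables in two directions give 4 × 2 = 8 possible limits. Six are set. Both missing limits are for low pressure.

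**Step 2: apply the rule to a low reading.** Take 70/40 mmHg as an illustration. Since 70 < 160 and 40 < 100, it meets neither pressure limit. The same holds for every reading below 160 systolic and below 100 diastolic, however low. No low pressure can bring a subject into the count.

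**Step 3: the listing.** It shows all observations, but only for subjects already flagged. A low pressure appears if the same subject also met a heart-rate, temperature or high-pressure limit. Otherwise it does not.

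**Step 4: compare with the protocol's TLS signs.** Three of the signs in Appendix G, Section 1 correspond directly to an SAP vital-sign variable.

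| Sign in Appendix G | Table 4 limit |
|---|---|
| Fever | temperature, high |
| Tachycardia | heart rate, high |
| Hypotension | none |

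**Step 5: other routes by which low pressure could be seen.**

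- Adverse events. Protocol 6.1.1.1 begins: "Laboratory abnormalities and changes in vital signs are considered to be adverse events only if they result in discontinuation from the study". The sentence then adds three further routes: a need for medical treatment, a protocol-specific criterion, or the investigator's own judgment. A symptomatic or treated fall would very plausibly be reported and tabulated under SAP 11.2. A low reading that needed no action and was not judged an event would not.
- Mean changes. SAP 11.3 summarises means, standard deviations and medians by scheduled visit. These describe the group and do not count individual falls.
- TLS searches. SAP Table 3 runs three searches on reported event terms, not on measured pressures. None of the individually named terms is hypotension. The documents do not give the content of the broad-scope query.

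None of these routes yields a count of subjects with a measured low pressure.

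**The case against.** The strongest reply is that nothing important is lost. A clinically relevant fall in pressure would meet one of the four routes in Protocol 6.1.1.1. Section 5.3.1.1 also has changes from baseline recorded on the adverse event form at each visit. TLS itself is assessed from event searches and laboratory data. This largely stands. What goes uncounted is mainly low readings that prompted no action and no adverse event report. The reply does not explain why heart rate and temperature get objective limits in both directions and pressure does not.

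A reader might infer that the trial's safety conclusion would be wrong in the drug's favour. The documents do not support that. In Appendix F hypotension counts only when attributed to hypocalcemia. The note below that table requires laboratory TLS plus raised creatinine, seizures, dysrhythmia or death, and hypotension is not in that list. A low reading alone identifies no TLS case. Nor does a table without a low row report that no subject had low pressure; it makes no statement either way.

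Three further criticisms of Table 4 are tempting and should not be pressed.

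- Temperature. The 38.5 °C limit might seem to conflict with "unexplained fevers > 38°C or 100.4°F". That phrase defines a B symptom in the complete remission criteria (Protocol 5.3.2.2.2). It is a response criterion, not a safety limit.
- Weight. The protocol's list reads "Vital signs include body temperature (oral or tympanic), weight, blood pressure and pulse", and the SAP leaves weight out. But the weight-loss figure of more than 10% is also a B symptom, judged over the preceding six months. It sets no safety limit that the SAP contradicts.
- Baseline. The SAP counts post-baseline values without regard to baseline status. This is a matter of preference. It can only raise the count, and excluding subjects who were abnormal at baseline could hide later worsening.

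**Conclusion.** The point holds as a gap in one descriptive table. Two of the eight possible limits are missing, both for low blood pressure, so the threshold count cannot show low pressure and the listing shows it only by coincidence with another flag. This is how the rule is written, so an analyst following the plan would produce the one-sided output.

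The effect is modest. The primary endpoint and the TLS analysis are untouched, and hypotension remains reportable as an adverse event. No number of affected subjects can be given, because the documents contain neither a low limit nor a rate of low readings.

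The conclusion assumes that Table 4 as read is complete. The low rows for heart rate and temperature are present, and nothing suggests that pressure rows are missing.

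**What to change.** Add a low row for systolic pressure and a low row for diastolic pressure to SAP Table 4, using the sponsor's own standard analysis limits fixed before the data are analysed. Count subjects with at least one post-baseline value meeting them, and include those subjects in the listing. If the omission is deliberate, state the reason in SAP 11.3.2. These limits are flags for a summary table and imply no change in how subjects are managed.

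The cost is two table rows and a small programming change on data already collected. The downside is a few more subjects flagged and listed.

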11.3.3 ECG/2D Echocardiogram

For ECG testing, subjects were only required to have a screening and a final visit assessment. If an ECG was clinically indicated, additional measurement could have been performed. Only ECG results that were abnormal were collected in the database.

For 2D echocardiogram testing, subjects had a screening assessment if clinically indicated. If an echocardiogram was clinically indicated, additional measurement could have been performed.

Data from ECG or 2D Echocardiogram that were collected will be provided in data listings.

No analyses are planned given the limited collection of data.

Appendix A. List of Abbreviations

AE	Adverse Event
CLL	Chronic Lymphocytic Leukemia
CTC	Common Toxicity Criteria
CTCAE	Common Terminology Criteria for Adverse Events
DILI	Drug-Induced Liver Injury
DOR	Duration of Overall Response
ECOG	Eastern Cooperative Oncology Group
EORTC QLQ C30	European Organization for Research and Treatment of Cancer Quality of Life Core Questionnaire
EORTC QLQ CLL 16	European Organization for Research and Treatment of Cancer Quality of Life Core Questionnaire Chronic Lymphocytic Leukemia Module
EQ-5D-5L	EuroQoL 5 Dimension 5 Level Questionnaire
IWCLL	International Workshop for Chronic Lymphocytic Leukemia
MedDRA	Medical Dictionary for Regulatory Activities
NCI	National Cancer Institute
NCI-WG	National Cancer Institute-Working Group
ORR	Overall Response Rate
OS	Overall Survival
PD	Progressive Disease
PFS	Progression-free Survival
QA	Quality Assurance
QC	Quality Control
QD	Once Daily
SAP	Statistical Analysis Plan
SMQ	Standard MedDRA Query
TEAE	Treatment-emergent Adverse Event
TLS	Tumor Lysis Syndrome
TTP	Time to Progression
ULN	Upper Limit of Normal
